6.4.4 Vital signs

Vital signs are examined in accordance with the schedule of visits in Table 1, including body temperature, pulse, respiratory rate, and blood pressure.

Additional monitoring of vital signs is allowed based on standard clinical practice or clinical need, and shall be documented in the eCRF when an AE/SAE occurs (if applicable).

The time and date of measurement shall be documented in the appropriate section of the eCRF.

6.4.4.1 Pulse and blood pressure

The subject's blood pressure and pulse in the supine position is measured after rest for at least 5 minutes. Two or more readings shall be done with 2-minute intervals and the readings shall be averaged. If the first two systolic blood pressure readings differ by more than 5 mmHg, measure again and average the readings. The time and date of measurement shall be documented in the appropriate section of the eCRF.

Pulse and blood pressure shall be measured prior to the administration of investigational drug.

6.4.4.2 Body temperature and respiratory rate

Collect the body temperature and respiratory rate prior to the infusion on the scheduled administration day.

6.4.5 Weight and height

Height is only measured during screening. Weight is measured during screening and at the end of treatment.

6.4.6 Pregnancy test

Urine or serum β human chorionic gonadotropin (β -HCG) pregnancy test must be performed in women of childbearing potential (refer to Section 4.3 for definition) within 3 days prior to the first dose of study treatment. If the result of urine β -HCG is positive or inconclusive, then serum β -hCG pregnancy test shall be performed. The conclusion shall be based on the serum pregnancy test. If the β -hCG result is positive, the subject is not eligible or must discontinue participating in the study. A repeated test shall be performed if pregnancy is suspected during the study.

6.4.7 Other safety examinations include the followings:

- Hepatitis B panel (HBsAg, HBsAb, HBcAb, HBeAg, and HBeAb).
- HIV antibody, HCV antibody (if the result shows HCV antibody positive, then HCV RNA test shall be further conducted).
- Thyroid function: T3, T4, TSH, FT3, and FT4. T3, T4, FT3, FT4, and TSH shall be tested during screening and prior to the administration of IBI308 from Cycle 2 onwards.

6.5 Immunogenicity

Immunogenicity assays will be carried out within 1 hour prior to IBI308 administration in Cycles 1, 2, 4 and then every 4 cycles thereafter (Cycle 8, 12, 16, and so on), and during safety follow-up. Tests shall be conducted at the central laboratory.

Anti-drug antibody (ADA) titer shall be tested for each subject. ADA-positive specimens shall be further tested for neutralizing antibodies (NAbs).

For ADA and NAb assays, 4 mL of whole blood is collected using vacutainers with clot activator. Serum is then separated, dispensed in aliquots, and frozen.

Refer to the Laboratory Manual provided by the sponsor-designated central laboratory for sampling methods, sample storage, transport, and analysis.

6.6 Quality of Life Evaluation

Quality of life evaluation will be performed on the day of the first dose, during each imaging evaluation, and during the end-of-treatment visit as per EQ 5D-5L and EORTC QLQ-C30.

EQ-5D-5L is a standardized tool used for patients to self-report their health status. Subjects will fill out a questionnaire that consists of 5 levels (no problems, slight problems, moderate problems, severe problems, and extreme problems) and 5 dimensions (mobility, self-care, usual activities, pain/discomfort, and anxiety/depression). A single EQ-5D health status is defined after combining the different levels of all 5 dimensions. In addition, subjects will mark on a visual analog scale (VAS) for their health status, which ranges from 0 (the imaginable worse state) to 100 (the best imaginable state).

The EORTC QLQ-C30 is a core questionnaire for patients with cancer consisting of 30 items which are divided into 15 scales: 5 functional scales (physical, role, cognitive, emotional, and social function), 3 symptom scales (fatigue, pain, and nausea/vomiting), 1 global health status/quality of life scale, and 6 single item scales.

6.7 Biomarker analysis

If permitted by the EC, all the eligible subjects must provide tumor tissue during screening. Acceptable tumor tissue include 8–10 unstained sections (4–5 μm) of archival specimen or fresh specimens for evaluations of PD-L1 expression, RNA expression and number of TIL.

EBV DNA copy number in plasma and peripheral blood lymphocytes shall be tested on the day of IBI308 administration in each cycle, with 4 mL of blood collected each time, until the end of study treatment. Tests shall be conducted at the central laboratory. According to the changes of

patients' condition and the needs of efficacy evaluation, EBV DNA test may be added by investigators at the centre. Ten mL whole blood samples are required to be provided by subjects for molecular tumor testing at the following time points: during screening, during efficacy evaluation but before the next treatment, and when PD is confirmed. The followings may be tested to predict anti-PD-1 treatment efficacy and prognosis of subjects: lymphocyte (T cell and NK cell) phenotyping and immune-related cytokines (TNF- α , IL-6, IL-15, soluble PD-L1 et al.) in different subtypes.

Refer to Laboratory Manual for details regarding sample processing, handling, and transport.

6.8 Storage and Destruction of Biological Samples

Samples will be disposed or destroyed, pooled and anonymized. Additional analyses of pooled and anonymized samples may be performed to further evaluate and validate the analytical method. Results of these analyses may be published separately from the Clinical Study Report (CSR).

Reproducibility (if performed) will be assessed simultaneously with the biological analysis of the samples. The results of these evaluations will not be published in the clinical study report, but will be presented separately in a biological analysis report.

7 Safety Reports and AE Management

7.1 Definition of AEs

An AE is defined as any adverse medical event that occurs after the signing of the informed consent form within 90 days since the last dose of the study treatment, regardless of whether or not considered as related to the study drugs. AEs include but are not limited to the followings:

- Worsening of pre-existing (prior to enrollment) medical conditions/diseases (including symptoms, signs, and laboratory abnormalities);
- Any new adverse medical conditions (including symptoms, signs, and newly diagnosed diseases);
- Clinically significant laboratory abnormalities.

7.2 Definition of SAEs

An SAE refers to an AE meeting at least one of the followings:

- Results in death, except for death caused by PD.

- Life-threatening (a life-threatening event is defined as an AE when the subject is at immediate risk of death at the time, but does not include the one that may lead to death only when the event worsens).
- Requires hospitalization or prolonged hospitalization, excluding the followings:
 - ✓ Hospitalization at a rehabilitation institution
 - ✓ Hospitalization at a sanatorium
 - ✓ General emergency admission
 - ✓ Day surgery (e.g. outpatient/same-day/ambulatory surgery)
 - ✓ Hospitalizations or prolonged hospitalizations unrelated to worsening of an AE are not considered as an SAE. For example: hospitalization due to pre-existing disease, without new AEs and exacerbation of pre-existing disease (e.g. hospitalization to examine laboratory abnormalities that have been persistent before the study starts); hospitalization for administrative reasons (e.g. annual routine physical examinations); hospitalizations during the study as specified in the protocol (e.g. hospitalization performed in accordance study protocol); elective hospitalization unrelated to worsening of AEs (e.g. elective surgery); scheduled treatment or surgical procedures, which shall be documented in the entire study protocol and/or individual subject's baseline information; and hospitalization merely due to the use of blood products.
- Results in permanent or serious disability/incapacity.
- Results in congenital anomalies/birth defects
- Other important medical events: defined as events that may jeopardize the subjects and require medical or surgical interventions to prevent one of the other outcomes listed in the definition above.

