3.2.5 Rationale for treatment after PD

Clinical data from approved products showed that a small number of subjects receiving immunotherapy may benefit clinically despite of preliminary evidence of PD (based on routine response criteria) prior to achieving objective response and/or stable disease [27, 28]. This phenomenon can be explained by two possibilities. First, increased inflammation in tumors may lead to increase of tumor volume, manifested as elevated measurable lesions and emergence of new, visible, non-measurable lesions. Over time, the malignant and inflammatory parts of the mass may shrink, resulting in significant imaging response and improvement in clinical signs. Second, in some patients, the initiation of anti-tumor immune response is slow, and tumor inhibition in the early stages is less than the tumor growth. Over time, anti-tumor activity will dominate, giving rise to imaging response and improvement in clinical signs. In Checkmate 205, a reduction in tumor burden after continuing treatment was observed in 6 of 9 cHL subjects with PD [27]. Response after pseudo-progression has also been seen in subjects with renal carcinoma during treatment with immune checkpoint inhibitors [28]. A small--sample-size study conducted at the University of Hong Kong involving pembrolizumab for the treatment of ENKTL-NT also had 1 subject who achieved CR after pseudo-progression [26]. Thus, subjects treated with IBI308 treatment may continue to receive the study treatment after being initially assessed to have PD by the investigator according to the Lugano 2014 Criteria, provided the subject is will benefit clinically and can tolerate the drug (see Section 5.1.2). Subjects must discontinue the study treatment if there are further evidence of PD.

4 Study Population

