6.3 Imaging Evaluation

Baseline evaluation is conducted within 28 days prior to the first dose of the study treatment. The investigator can evaluate the imaging results within 28 days prior to the enrollment.

PET-CT and contrast-enhanced CT will be used (MRI will be performed for subjects allergic to CT contrast media). PET-CT shall be performed at baseline, week 6 (± 7 days), week 15 (± 7 days), and week 24 (± 7 days). PET-CT evaluation shall be performed at the end of treatment for subjects who discontinue the treatment prematurely prior to week 24 (unless the previous PET-CT scan is done within the past month). Contrast-enhanced CT shall be performed at baseline, week 24 (± 7 days), every 12 weeks (± 14 days) after 24 weeks, and every 24 weeks (± 14 days) after 48 weeks initiation of new anti-tumor therapy, PD, withdrawal of ICF, or death. Unplanned PET-CT and contrast-enhanced CT shall be added to evaluate the efficacy when investigators deem appropriate, if the subjects agree. The examinations will be taken at sponsor's expense. First PD shall be confirmed after 4–6 weeks. For subject who discontinue the treatment for reasons other

than PD, tumor imaging evaluation shall be continued according to the study protocol until initiation of new anti-tumor therapy, PD, withdrawal of ICF, or death.

Imaging data shall be copied or saved according to the requirements of the sponsor.

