Generally, AEs secondary to other events (such as result of another event or clinical sequelae) shall be documented as the primary event, unless the event is severe or an SAE. However, clinically significant secondary events shall be recorded as independent adverse events in the eCRFs if they occur at different time than the primary event. If the relationship between events is unclear, document them as separate events in the eCRFs.

Ongoing or recurrent AEs

An ongoing AE refers to an event that does not resolve and is ongoing between two assessment time points. These AEs shall only be documented once in the eCRFs. The initial severity shall be documented, and the information shall be updated if the event exacerbates.

Recurring AEs refer to AEs that have resolved between the two time points of assessment but subsequently occur again. These events shall be independently documented in the eCRFs.

Laboratory abnormalities

Any clinically significant laboratory abnormalities shall be reported as AEs. The investigator is responsible for reviewing all the laboratory abnormalities, and determine whether the findings shall be reported as AEs.

Death

During the entire course of the study, all the deaths that occur within 90 days after the last dose shall be documented in the eCRFs and Mortality Report Form and reported to the sponsor timely, regardless of the causality with the study drugs.

If the cause of death is known, record the cause of death as an AE and the outcome of the event as a death and submit an SAE report; if the cause of death is unclear, the AE shall be recorded as Death of Unknown Cause in the AE form, and submit the SAE report as Death of Unknown Cause. The exact cause of the death shall be further investigated.

If the cause of death is confirmed to be PD, then the event shall not be documented and reported as an AE/SAE. However, the event shall be documented in the Mortality Report Form of the eCRF and reported to the sponsor timely.

Pre-existing medical conditions

Symptoms/signs present during the screening period will be recorded and reported as AEs only if their severity, frequency, or property becomes aggravated (except for worsening of the studied disease). The relative changes shall be documented, such as increased frequency of headaches.

Hospitalization and prolonged hospitalization, or surgery

Any AEs leading to hospitalization or prolonged hospitalization shall be recorded and reported as SAEs, with the following exceptions:

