- Hospitalization or prolonged hospitalization as required by study protocol (such as for dose administration or efficacy evaluation).
- Hospitalization due to a pre-existing medical condition that remains stable, e.g. elective

surgery/therapy scheduled prior to the study.

However, elective surgery/therapy required because of the exacerbated condition during the study (e.g. surgery/therapy required earlier than scheduled) shall be considered as an AE.

PD

PD is defined as the worsening of subject condition caused by the primary tumor that the study drug is targeting, the appearance of new lesions, or the progression of the primary lesion. PD will not be reported as an AE. Any deaths, life-threatening events, hospitalization or prolonged hospitalization, permanent or significant disability/incapacity, congenital anomaly/birth defects, or other important medical events caused by PD will not be reported as an SAE.

Overdose

An overdose is the administration of a drug at more than the dose specified in the study protocol. All the occurrences of overdose must be documented in the eCRF.

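### Sections 7.2 and 7.5.3 classify emergency admissions differently, and the exemption for non-fatal serious events due to PD does not require PD to be confirmed

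*Protocol*

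**What the plan says.** **Hospitalization.** Protocol Section 7.2 lists hospitalization as a seriousness criterion and then removes several kinds of stay from it: rehabilitation institutions, sanatoria, "General emergency admission", day surgery, and a final group introduced by "Hospitalizations or prolonged hospitalizations unrelated to worsening of an AE are not considered as an SAE". The last example in that group is "hospitalization merely due to the use of blood products". The emergency item has no definition or qualifier.

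Section 7.5.3, under its hospitalization heading, gives a different rule: "Any AEs leading to hospitalization or prolonged hospitalization shall be recorded and reported as SAEs, with the following exceptions". Two exceptions follow: stays that the protocol requires, and stays for a pre-existing condition that remains stable.

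**PD.** Among the seriousness criteria in Section 7.2, only death carries a PD exception: "Results in death, except for death caused by PD". The PD paragraph of Section 7.5.3 goes further. PD is not reported as an AE, and its exemption runs through deaths, life-threatening events, hospitalization and disability, ending "or other important medical events caused by PD will not be reported as an SAE". The death paragraph of the same section is stricter: a death is left out of AE and SAE reporting only when PD has been confirmed as its cause, and it still goes on the mortality form.

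**Timing and pseudo-progression.** Section 7.6 requires the SAE report within 24 hours of noticing the event. Section 6.3 says "First PD shall be confirmed after" 4–6 weeks. Section 3.2.5 explains that "increased inflammation in tumors may lead to increase of tumor volume", and the Summary of Amendment reports several early PDs and difficulty with pseudo-progression among the 28 subjects enrolled at that point.

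**The concern.** SAE status triggers the 24-hour report to the sponsor, the regulator and the ethics committee. It also feeds the summaries of treatment-emergent and treatment-related SAEs in SAP Section 5.6.1, and it contributes to the safety review of the first 20 subjects, which can stop the study (Protocol Section 8.5). If two sections give different answers for the same admission, classification depends on which one the site reads.

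The affected admissions matter for this drug. Immune-related events such as pneumonitis can need unplanned admission; Appendix 7 lists hospitalization in its guidance for grade 3–4 pneumonitis. Section 7.3 describes grade 3, for terms outside CTCAE, as severe but not immediately life-threatening, with hospitalization indicated. For such events the life-threatening criterion does not help, and hospitalization is the main objective route to SAE status.

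The PD exemption raises a different problem. An inflammatory flare of the tumor can look like progression. If the site attributes its consequences to PD, the exemption applies at a time when the trial's own rules do not yet treat the PD as confirmed.

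**Working it through.** No arithmetic decides this point, apart from one comparison of times in step 2. The check compares the rules item by item.

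**1. Hospitalization exceptions**

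| Type of stay | Section 7.2 | Section 7.5.3 |
|---|---|---|
| Emergency admission | Excluded, undefined | No exception: SAE if an AE led to it |
| Rehabilitation, sanatorium, day surgery | Excluded | Not listed |
| Blood products only | Excluded, within the group not linked to a worsening AE | Not listed |
| Required by the protocol | Excluded | Excepted |
| Stable pre-existing condition | Excluded | Excepted |

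Take a subject with a new AE who is admitted to hospital as an emergency. Read literally, Section 7.2 says the stay does not count toward the hospitalization criterion. Section 7.5.3 says the event is an SAE. Nothing in either section says which one governs.

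**2. PD exemption**

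- *Scope.* Section 7.2 exempts deaths only. Section 7.5.3 adds all the non-fatal seriousness criteria.
- *Standard of proof.* For deaths, Section 7.5.3 requires PD to be confirmed as the cause. For non-fatal events it states no such condition.
- *Timing.* Confirmation of a first PD takes 4 × 7 = 28 to 6 × 7 = 42 days; the SAE report is due within 1 day. For an event noticed on the day of the first PD finding, the report falls due 28 − 1 = 27 to 42 − 1 = 41 days before confirmation.
- *Knock-on effect.* Section 5.4 classes an event as immune-related only if no alternative cause, PD among them, is found. Attribution to PD therefore removes the immune-related label and, with it, the item for suspected immune-related events of grade 3 or above in the list of AEs of special interest (Section 7.8.2). Because PD itself is not an AE, there may be no AE record either.

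**3. What still catches the event**

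- Under step 1, the AE is still collected up to 90 days after the last dose (Section 7.5.1) and graded. It is flagged as of special interest if it meets Section 7.8.2. The life-threatening, disability and important-medical-event criteria stay open. What can be lost is SAE status and the 24-hour report. Section 7.8.2 sets no expedited time limit, so the flag does not replace that report.
- Under step 2, these safeguards work only if the event is first recognised as something other than PD.

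**The case against.** The strongest reply is that the emergency item stands beside rehabilitation, sanatorium and outpatient surgery. In a translated protocol it may well mean attendance at an emergency department without an inpatient stay, and on that reading the conflict disappears. This is plausible, but the text says admission and defines nothing, so the reply supports rewording rather than leaving the text alone.

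On PD, the exemption covers events that PD caused, not events of uncertain cause. Section 7.4 has a category for causality that cannot be determined, SAP Section 5.6.1 counts undetermined causality as related, and Section 7.6 provides for follow-up reports. The 4–6-week rule concerns imaging and was not written for safety attribution. All of this stands. It does not supply the missing condition, and the tools for uncertain causality come into play only once the event has been reported as an AE.

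Some stronger readings are tempting but not supported:

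- *That Section 7.2 exempts serious events around an unconfirmed PD and so contradicts 7.5.3.* The wide exemption is in 7.5.3 itself; 7.2 exempts only deaths. Nor does any text name unconfirmed PD. Its inclusion is inferred from the absence of a condition.
- *That admission to transfuse a new cytopenia is exempt.* The item is limited to stays merely for blood products, within a group not related to a worsening AE. A new cytopenia can itself be an AE under Section 7.1.
- *That serious toxicity leaves no trace.* For emergency admissions, AE collection remains, and deaths within 90 days of the last dose go on the mortality form whatever their cause.

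**Conclusion.** There are two separate defects, and both should be fixed. First, a new AE that leads to an emergency inpatient admission is treated differently by Sections 7.2 and 7.5.3. Second, the exemption in 7.5.3 for non-fatal events due to PD is wider than 7.2 and looser than the section's own rule for deaths, in a trial whose protocol expects pseudo-progression.

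The first affects SAE classification and expedited reporting, not whether the AE is collected. The second can also affect AE and immune-related recording when an event is wrongly attributed to PD.

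The size of any under-count cannot be estimated. A reader might infer one from the phase Ia data in Section 1.2.2, where 3 possibly related cases of pneumonitis or lung infection were seen among 12 subjects. That count comes from subjects with solid tumors across four dose cohorts. It says nothing about how often such events lead to emergency admission, are attributed to PD or are left unreported.

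The first defect rests on reading the emergency item literally. The second rests on sites applying the exemption to a first PD before it is confirmed, which the text permits but does not direct.

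**What to change.** 1. Make the exception lists in Sections 7.2 and 7.5.3 identical, or keep one list and refer to it from the other section.
2. Replace the emergency item with an emergency-department visit that does not result in inpatient admission.
3. Add to the non-fatal PD exemption the confirmation condition already used for deaths. An event that meets a seriousness criterion between a first PD and its confirmation would then be reported as an SAE with a causality assessment, and could be re-attributed in a follow-up report.
4. State that admission for a new or worsened cytopenia is not covered by the blood-product item. This is a clarification only.
5. Re-screen the hospitalizations already recorded in the database against the reconciled list.

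The cost is protocol wording, a memo to sites, a database query and a few more SAE reports, some of them later re-attributed to PD. No new visits or tests are needed.
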